1. PROTOCOL SYNOPSIS

Investigational Product	SCS trial stimulator (Model 1000)
Title	A single-arm, open label, single center, prospective study of an ultra-high frequency spinal cord stimulation for treatment of chronic back pain or lower limb pain
Objectives	
Primary:
 
 ● To assess the analgesic effectiveness of ultra-high frequency spinal cord stimulation (as measured by VAS score compared to baseline) ● To evaluate safety of ultra-high frequency spinal cord stimulation by identifying the incidence rate of adverse events (AEs) and serious adverse events (SAEs) during the trial 
Secondary:
 
 ● The change from baseline in functionality using the BPI/ODI evaluations ● To determine the presence or absence of stimulation-induced paresthesia. ● To assess the change of pain medication consumption
Indication	Pain control
Design	This study is a prospective, single-arm, open label, single center to confirm the effectiveness and safety of an ultra-high frequency spinal cord stimulation in patients with chronic back pain or lower limb pain.
Population	
Inclusion criteria
 
 1. Age ≥ 20 and ≤ 75 2. Have a symptom of back or lower limb pain with a diagnosis related to spinal lesion, herniated disc, nerve injury, stenosis, failed back surgery syndrome (FBSS), complex regional pain syndrome (CRPS) or ischemic lower limb pain and have pain history of ≥ 6 months. 3. Have an average pain score >5 by Visual Analogue Scale

	
(VAS) on inclusion.
 
4. Has failed to achieve adequate pain relief from prior pharmacologic treatments.5. In the judgement of the investigator, the subject is an appropriate candidate for the trial procedure.6. The subject is willing and able to comply with the procedure and requirements of this trial.7. The participant is able to understand and provide informed consent, and has signed their written informed consent in accordance with IRB requirements. 
Exclusion criteria
 
1. Have evidence of a mental or psychological condition that affects pain perception and has difficulty/disability performing objective pain assessment, or have previously failed mental or psychological assessments administered by a psychiatrist that may be deemed to indicate the subject's lack of suitability for participation in this study.2. Subject has exhibited unstable pain condition within the past 30 days as interviewed by Investigator.3. Be on anticoagulant medication with INR >1.5 or platelet count less than 100,000/μL, peripheral vascular diseases (PVDs), visceral pain or uncontrolled Diabetes mellitus (DM).4. Has had corticosteroid therapy at an intended site of stimulation within the past 30 days.5. Pain medication(s) dosages(s) are not stable for at least 30 days at investigator's discretion.6. Currently has an active implantable device including ICD, pacemaker, spinal cord stimulator or intrathecal drug pump or subject requires magnetic resonance imaging (MRIs) or diathermy.7. Have a current diagnosis of cancer with active symptoms.8. Have a known terminal illness with life expectancy less than one year.9. Have a systematic or local infection, which may increase study risk.
--	---

	
10. Currently has an indwelling device that may pose an increased risk of infection.
 
11. Be pregnant or breast feeding.
 
12. Have a medical history of drug or alcohol addiction within the past 2 years.
 
13. Participation in any investigational study in the last 30 days or current enrollment in any trial.
 
14. Be currently involved in an injury claim law suit or medically related litigation, including workers compensation.
 
15. Be a prisoner.

Sample Size	10 evaluated subjects
Study Duration	14 (+1) days
Efficacy Data	
Primary endpoint:
 
 ● Analgesic effectiveness of ultra-high frequency spinal cord stimulation (as measured by VAS score compare to baseline) ● Adverse event (AE) and serious AE (SAE) incidence rates during the trial 
Secondary endpoints:
 
 ● Change in BPI/ODI compared to baseline ● Incidence of stimulation-induced paresthesia ● Change in pain medication consumption, including Non-Steroidal Anti-Inflammatory Drugs (NSAIDs) and weak opioids, compared to baseline
Statistical Procedures	
All data will be analyzed according to the full analysis set principle, including patients who received at least one dose of study treatment and had at least one follow-up evaluation regardless of their compliance with the protocol. Repeated measures analysis of variance (ANOVA) will be adopted to examine whether there are changes in VAS/BPI/ODI scores and pain medication consumption during the trail. The frequent endpoints in this study include AE, SAE and incidence of paresthesia of stimulation-induced. The incidence rates and their 95% confidence interval (CI) will be estimated. A Last Observation Carried Forward (LOCF)

	
method will be used to define endpoints if data is unavailable at the analysis time point; the last available measurement prior to the visit will be used to fill in the missing data. Interim analysis with Pocock-type group sequential plan will be undertaken for the likelihood of no merging trends and no reasonable chance of demonstrating benefit after 5 subjects are enrolled. The statistical significant level will be set at a two-tailed type 1 error of 0.05.

--	---

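### The only analysis set in the synopsis requires a follow-up evaluation, so a treated subject who has an adverse event and leaves before follow-up could drop out of the primary AE/SAE incidence

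*Combined protocol and SAP*

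**What the plan says.** All references are to section 1, Protocol Synopsis, of the combined protocol and SAP.

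- **Objectives.** Safety is a primary objective, to be assessed "by identifying the incidence rate of adverse events (AEs) and serious adverse events (SAEs) during the trial".
- **Efficacy Data.** Listed under the primary endpoint, beside VAS, is "Adverse event (AE) and serious AE (SAE) incidence rates during the trial".
- **Statistical Procedures, scope.** "All data will be analyzed according to the full analysis set principle".
- **Statistical Procedures, membership.** The set is described as "including patients who received at least one dose of study treatment and had at least one follow-up evaluation". Non-compliance with the protocol does not exclude a subject.
- **Statistical Procedures, safety analysis.** In the same paragraph, AE and SAE are named among the endpoints to be summarised as frequencies, and "The incidence rates and their 95% confidence interval (CI) will be estimated". No separate denominator is given.
- **Statistical Procedures, missing data.** Under LOCF, "the last available measurement prior to the visit will be used to fill in the missing data".
- **Sample Size and Study Duration.** The target is 10 evaluated subjects over 14 (+1) days. The synopsis gives no dropout allowance, no replacement rule and no date for the first follow-up evaluation.

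**The concern.** A follow-up condition is understandable for change scores, since a VAS, BPI or ODI change cannot be computed without a post-baseline value. Adverse event incidence does not need one: a subject is at risk once treated, and an event counts whether or not a later evaluation takes place.

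Applied to AE and SAE incidence, the condition makes entry to the analysis depend on something the outcome can influence. A subject who has a complication and leaves early may be absent because of the very event the endpoint is meant to count. Dropping that subject lowers the rate. Dropping an early leaver who had no event raises it slightly. If nobody leaves early, nothing changes.

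What is at stake is one of the trial's primary results, the reported safety estimate and its interval. The synopsis states no safety threshold or decision that uses the rate, so the consequence goes no further than that.

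**Working it through.** The synopsis states no figure on this point, so there is none to reproduce. The check has two parts.

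**1. Does the text exclude such a subject?** Take a subject who is treated, has an event and leaves before any follow-up evaluation.

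- *Membership.* The two conditions, treatment and a follow-up evaluation, are joined by *and*. The subject meets the first and fails the second.
- *Scope.* The set governs all data, and AE and SAE rates are described in the same paragraph without another set. The exclusion therefore reaches the primary safety endpoint.
- *Compliance clause.* It waives protocol compliance. It does not waive the follow-up condition.
- *LOCF.* It fills a missing measurement from an earlier one. It does not change who is in the set.

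Nothing in the paragraph brings the subject back, unless the contact at which the event was recorded itself counts as a follow-up evaluation. The synopsis does not define the term.

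**2. How much could one subject matter?** Input from the synopsis: 10 evaluated subjects and 95% intervals. Assumed: the event counts, the number of early exits, and exact (Clopper-Pearson) intervals, since the synopsis names no interval method.

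For x events in n subjects the 95% limits are

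- lower = Beta quantile at 0.025 with parameters (x, n − x + 1), or 0 if x = 0;
- upper = Beta quantile at 0.975 with parameters (x + 1, n − x).

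For x = 0 the upper limit reduces to 1 − 0.025^(1/n). With n = 10 this is 1 − 0.025^(0.1) = 0.3085.

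One early leaver is excluded in each row:

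| Scenario (assumed) | Set as written | All treated |
|---|---|---|
| SAE in the leaver only; 10 evaluated still reached | 0/10 = 0% (0 to 30.8%) | 1/11 = 9.1% (0.2 to 41.3%) |
| SAE in the leaver only; 10 treated in total | 0/9 = 0% (0 to 33.6%) | 1/10 = 10.0% (0.3 to 44.5%) |
| Any AE: three in the others, one in the leaver; 10 evaluated | 3/10 = 30.0% (6.7 to 65.2%) | 4/11 = 36.4% (10.9 to 69.2%) |
| Any AE: three in the others, one in the leaver; 10 treated | 3/9 = 33.3% (7.5 to 70.1%) | 4/10 = 40.0% (12.2 to 73.8%) |
| Opposite direction: one SAE in the 10 evaluated, leaver event-free | 1/10 = 10.0% (0.3 to 44.5%) | 1/11 = 9.1% (0.2 to 41.3%) |

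Excluding a leaver with an event lowers the estimate by 9.1 or 10.0 percentage points in the SAE rows, and by 36.4 − 30.0 = 6.4 or 40.0 − 33.3 = 6.7 points in the any-AE rows. Excluding an event-free leaver raises it by 10.0 − 9.1 = 0.9 points. The intervals overlap widely in every row.

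**How often might it happen?** Let p be the chance that a treated subject both has an event and leaves before follow-up. The chance that at least one of 10 treated subjects is affected is 1 − (1 − p)^10:

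- p = 1%: 1 − 0.99^10 = 9.6%
- p = 5%: 1 − 0.95^10 = 40.1%
- p = 10%: 1 − 0.90^10 = 65.1%

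The synopsis supports no particular value of p. With no date for the first follow-up evaluation, the length of the exposed period cannot be worked out either.

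**The case against.** The case against is mainly about how much follows from a short text.

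- *Only a synopsis.* A safety or all-treated set may be defined in a fuller protocol or SAP section that was not available for this review. If so, the repair shrinks to a cross-reference. This stands as a limit on the finding.
- *An undefined term.* An event enters the numerator only if someone recorded it. If that contact counts as a follow-up evaluation, the subject stays in and nothing is lost. This also stands, though an event recorded during the procedure itself might still not qualify. Without a definition, the choice could be made after the event is known, in an open-label study, which is a reason to settle it beforehand.
- *Several conditions must coincide.* There must be no safety set elsewhere, a narrow reading of the term, an exit before the first evaluation in a study of 14 (+1) days, and an event in that subject. The last two have no stated frequency, and the 10% value of p is hard to support.
- *Small numbers.* With about 10 subjects, one subject always moves a rate noticeably, so part of the illustration only shows imprecision. But imprecision is carried by the interval. Removing a subject because of the outcome is a bias, which the interval does not reflect, and reporting no SAE is different in kind from reporting one.
- *No decision depends on the rate.* True for the synopsis. This limits the severity but does not justify an outcome-dependent denominator for a primary endpoint.

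**Conclusion.** The concern holds, within the synopsis. The stated rule, and not merely a missing detail, can leave a treated subject with an event out of the primary AE/SAE incidence, and neither the compliance clause nor LOCF restores that subject.

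The size depends on assumed counts. One excluded subject with an event moves the estimate down by roughly 6 to 10 percentage points in the scenarios shown, and can turn an SAE rate of 9 to 10% into 0%. An event-free early leaver moves it up by about 1 point. With no early leavers there is no effect.

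The conclusion rests on two conditions: no other safety set is defined elsewhere, and the contact that records the event is not itself a follow-up evaluation. This should be fixed, with moderate confidence. It affects a primary estimate, but no stated decision.

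**What to change.** Keep the full analysis set for VAS, BPI, ODI and pain medication consumption. Add to Statistical Procedures a statement to this effect:

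> AE and SAE incidence and their 95% CIs are calculated in all treated subjects, whether or not a follow-up evaluation took place and whether or not they count among the 10 evaluated subjects.

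Two definitions should go with it. The sponsor should say when treatment starts for this device. It should also state in advance whether subjects in whom the procedure began but stimulation was never delivered are counted; that choice is the sponsor's. If the full protocol already defines such a set, the synopsis need only refer to it. No change to the paresthesia denominator is proposed.

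The cost is one or two sentences, with no extra subjects or visits. The reported incidence may come out higher if an early leaver had an event, or slightly lower if an early leaver had none.

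### AE and SAE rates are tied to an efficacy-type analysis set with an undefined dose condition, so a subject harmed before stimulation is delivered could drop out of the primary safety rate

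*Combined protocol and SAP*

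**What the plan says.** All the relevant text is in section 1 (Protocol Synopsis) of the combined protocol and SAP.

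- **Scope of the analysis set (Statistical Procedures).** "All data will be analyzed according to the full analysis set principle". No separate safety set is named, and adverse events are not exempted.
- **Entry conditions (same sentence).** There are two: "including patients who received at least one dose of study treatment" "and had at least one follow-up evaluation regardless of their compliance with the protocol".
- **Primary safety endpoint (Efficacy Data).** "Adverse event (AE) and serious AE (SAE) incidence rates during the trial". Statistical Procedures adds: "The incidence rates and their 95% confidence interval (CI) will be estimated". The interval method is not named.
- **The procedure (Population).** Inclusion criterion 5 asks the investigator to judge that "the subject is an appropriate candidate for the trial procedure". The steps of that procedure, and their timing relative to first stimulation, are not described. Exclusion criterion 3 begins "Be on anticoagulant medication with INR >1.5 or platelet count less than 100,000/μL".
- **Sample size.** "10 evaluated subjects". The number to be enrolled and any rule on replacing subjects are not given.

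**The concern.** A dose is a drug-trial unit. Here the product is a stimulator, and the text does not say whether study treatment begins with the procedure or with the first delivered stimulation. If it begins with stimulation, a subject who has an AE or SAE during the procedure, and in whom stimulation is then never delivered, has received no dose. That subject leaves both the numerator and the denominator of a primary endpoint.

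The second entry condition points the same way. A subject who is harmed early and leaves before any follow-up evaluation is excluded however a dose is defined.

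Both conditions are ordinary for an efficacy set, because a subject without treatment or a later measurement contributes nothing to a change from baseline. For safety they are unsuitable: the event being counted may be the reason why the subject fails to qualify. With about ten subjects, one omission can decide whether the report says that there were no SAEs. Because the terms are undefined, two analysts could also build different denominators from the same plan, and could do so after seeing the events.

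**Working it through.** **The plan's own figure.** The only relevant number is 10 evaluated subjects. It cannot be reproduced, because no effect size, standard deviation, expected event rate, power or dropout is given. The check therefore concerns the denominator only.

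**Inputs.** From the plan: n = 10 in the analysis set, and the 95% confidence level. Assumed: the number x of analysed subjects with an event, the number k of excluded subjects with an event, and exact Clopper-Pearson intervals.

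**Step 1: restore the excluded subjects.** The rate as planned is x/n. Counted from the start of the procedure it is (x + k)/(n + k).

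| x | Planned set | One excluded subject with an event restored | Difference (points) |
|---|---|---|---|
| 0 | 0/10 = 0% (0 to 30.8%) | 1/11 = 9.1% (0.2 to 41.3%) | +9.1 |
| 1 | 1/10 = 10.0% (0.3 to 44.5%) | 2/11 = 18.2% (2.3 to 51.8%) | +8.2 |
| 2 | 2/10 = 20.0% (2.5 to 55.6%) | 3/11 = 27.3% (6.0 to 61.0%) | +7.3 |
| 5 | 5/10 = 50.0% (18.7 to 81.3%) | 6/11 = 54.5% (23.4 to 83.3%) | +4.5 |
| 10 | 10/10 = 100% | 11/11 = 100% | 0 |

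For k = 1 the difference is (x + 1)/(n + 1) − x/n = (n − x)/[n(n + 1)]. At n = 10 and x = 0 this is 10/110 = 9.1 points. With k = 2 and x = 0 the restored rate is 2/12 = 16.7% (2.1 to 48.4%). With k = 0 there is no difference.

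**Step 2: direction when the excluded subject has no event.** The rate then moves the other way: 1/10 = 10.0% in the planned set against 1/11 = 9.1% with the subject restored. The entry rule as such has no fixed direction. The downward shift is specific to excluded subjects who had an event, and it occurs only if x < n.

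**Step 3: how likely is at least one such subject?** The documents give no rate, so an assumed per-subject probability p of harm before stimulation is varied. The chance of at least one in 10 is 1 − (1 − p)^10:

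- p = 1%: 9.6%
- p = 2%: 18.3%
- p = 5%: 40.1%
- p = 10%: 65.1%

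These figures assume that every such subject goes without stimulation. They are a range, not an estimate for this trial.

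**Step 4: would changing the dose clause alone be enough?** No. The follow-up condition stands in the same sentence. A subject harmed during the procedure who leaves before any follow-up evaluation would still be excluded. Both conditions have to be lifted for the safety rates.

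**The case against.** The strongest reply is that the plan speaks of study treatment, not of stimulation. If study treatment includes the procedure, the dose condition excludes nobody described here. This stands, and it is why the point is conditional. It does not remove the need to act, because the denominator of a primary endpoint should not depend on an undefined term, and the follow-up condition operates on either reading.

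A reader might also infer several stronger things that the documents do not support:

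- **That the plan recognises a hazardous step before stimulation.** The INR, platelet and infection criteria are consistent with an invasive step, but the text does not tie them to the procedure or describe an interval before first stimulation. The procedure may include the stimulation itself.
- **That the AE/SAE rate is understated.** It can be, if such a subject occurs and not every analysed subject already has an event.
- **That the error always favours the device.** Step 2 of the working shows the opposite for an excluded subject without an event. A failed placement, for example, need not be an AE.
- **That harmed subjects will be replaced unseen.** The sample-size entry states no replacement rule. The denominators of 11 and 12 are assumptions.

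Finally, the available text is a synopsis, so a safety population defined elsewhere cannot be ruled out. None appears here.

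**Conclusion.** The concern holds in conditional form. The only analysis set in the text governs the primary AE and SAE rates, and its two entry conditions can remove a subject who was harmed early. The dose condition does so only if a dose means delivered stimulation and harm can precede it; the follow-up condition does not depend on that reading and is the firmer of the two.

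One omitted subject with an event lowers the reported rate by at most 9.1 percentage points when ten subjects are analysed, and by less as more of the ten have events. The largest practical effect is at zero, where a report of no SAEs would replace a report of one. These sizes are illustrative, since the event counts are assumed. The wide intervals overlap heavily, so the issue is whether the event is counted at all, not precision. The point warrants a correction before analysis; it does not show that the safety result will be wrong.

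**What to change.** Add a separate safety set to Statistical Procedures and use it for AE and SAE incidence. Suggested wording:

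*The safety set comprises all subjects in whom the trial procedure was started, whether or not stimulation was delivered and with no requirement for a follow-up evaluation. AE and SAE incidence is estimated in this set, with events counted from the start of the procedure.*

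Report events before first stimulation and after first stimulation in separate rows. Keep the full analysis set for the efficacy endpoints, and define there what a dose of study treatment means for this device. Keep delivered stimulation as a condition for the paresthesia rate, where it belongs.

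The cost is small: one sentence for the set and its counting rule, a line of definition, and one extra table row. The downside is that the reported AE/SAE rate may be slightly less favourable.

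### The analysis set leaves out treated subjects with no follow-up evaluation, which can inflate the uncontrolled VAS change and, as written, also filters the co-primary AE/SAE rates

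*Combined protocol and SAP*

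**What the plan says.** All of the relevant text is in section 1, Protocol Synopsis.

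- **Statistical Procedures, scope.** "All data will be analyzed according to the full analysis set principle". No endpoint is exempted.
- **Statistical Procedures, definition.** The set consists of patients who "received at least one dose of study treatment and had at least one follow-up evaluation". There are two conditions: treatment was received, and a follow-up evaluation exists. Non-compliance is not a reason for exclusion.
- **Statistical Procedures, missing data.** Under LOCF, "the last available measurement prior to the visit will be used to fill in the missing data".
- **Efficacy Data.** There are two primary endpoints: VAS compared with baseline, and "Adverse event (AE) and serious AE (SAE) incidence rates during the trial".
- **Sample Size.** "10 evaluated subjects". The count is of evaluated subjects, not of those enrolled or treated.
- **Design.** "This study is a prospective, single-arm, open label, single center". There is no comparator.
- **Study Duration.** 14 (+1) days.

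The synopsis gives no dropout rate, replacement rule, separate safety set, or sensitivity analysis for subjects who were treated but never evaluated.

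**The concern.** Having a follow-up evaluation is something that happens, or fails to happen, after treatment starts. Making it a condition of entry to the analysis selects subjects on a post-treatment event. A subject who starts stimulation and withdraws before any evaluation, because it did not help or was not tolerated, is the kind of subject whose result would pull the mean down.

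In a randomised trial both arms lose subjects under the same rule, which gives some protection. Here the estimate is a change from baseline in one group, so any selection passes straight into it. With about 10 subjects, one exclusion is material.

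The same filter reaches the other primary endpoint. If all data are analysed in this set, an adverse event in a treated subject who is never evaluated can drop out of both the numerator and the denominator of the AE/SAE rates.

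**Working it through.** **1. Who is excluded.** Three cases follow from the definition and the LOCF rule:

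| Subject | In the set? | Effect of LOCF |
|---|---|---|
| Treated, all evaluations done | Yes | None needed |
| Treated, at least one evaluation, then leaves | Yes | Last value carried forward |
| Treated, no post-baseline evaluation | No | None: LOCF fills gaps only for subjects already in the set |

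The problem is confined to the third row.

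**2. Size of the effect on the mean.** The plan's sample size of 10 cannot be reproduced, because no effect size, SD, power or dropout rate is given. The calculation does not need it. Let n subjects be kept with mean improvement m, and let k treated subjects be excluded with mean improvement c.

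- All-treated mean = (n·m + k·c)/(n + k).
- If c = 0, reported mean ÷ all-treated mean = (n + k)/n.

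Assumptions, none from the documents: c = 0, k = 1 to 3 and, for illustration, m = 3.0 VAS points.

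| k | 10 evaluated plus k excluded: all-treated mean | Overstatement | 10 treated, k excluded: all-treated mean | Overstatement |
|---|---|---|---|---|
| 0 | 3.0 | 0% | 3.0 | 0% |
| 1 | 30/11 = 2.73 | 11/10: 10% | 27/10 = 2.7 | 10/9: 11% |
| 2 | 30/12 = 2.50 | 12/10: 20% | 24/10 = 2.4 | 10/8: 25% |
| 3 | 30/13 = 2.31 | 13/10: 30% | 21/10 = 2.1 | 10/7: 43% |

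The percentages do not depend on m. They do depend on c: if c = m the bias is zero, and if excluded subjects worsened it is larger. With m = 3, c = −1 and k = 1 in 10 treated, the all-treated mean is (27 − 1)/10 = 2.6.

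**3. How likely it is.** For 10 treated subjects and an assumed per-subject probability d of having no follow-up at all, the chance of at least one such subject is 1 − (1 − d)^10. This is 18%, 40%, 65% or 89% for d = 2%, 5%, 10% or 20%.

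**4. Effect on the test.** A paired t-test was simulated at two-sided 0.05 with an assumed mean change of 1.75 and SD 2, as a simple stand-in for the planned repeated measures ANOVA.

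- With replacement: power is about 0.69 in the 10 kept, and 0.68 to 0.69 after adding one to three zeros.
- Without replacement, for k = 1, 2, 3: 0.64, 0.57, 0.49 in the kept set, against 0.63, 0.55, 0.47 with the zeros included.

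In both cases the choice of set hardly changes the test. What moves is the estimated size of the effect.

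**5. Effect on safety.** Suppose 10 are treated, one has no follow-up evaluation, and that subject has the only SAE. With exact (Clopper-Pearson) 95% intervals:

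- as written: 0/9, 0 to 33.6%;
- all treated: 1/10 = 10%, 0.3% to 44.5%.

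The intervals overlap heavily, but one report shows no SAE and the other shows one.

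**The case against.** Requiring treatment plus a post-baseline measurement is a familiar definition of a full analysis set, and it is stated openly. Follow-up lasts about two weeks at one centre, so few subjects may be lost before any evaluation, although the documents do not show this. The values of k and c are assumed. Setting the change to zero is itself single imputation and may be wrong for someone lost for unrelated reasons. These points stand; they limit the size and certainty of the concern without removing the gap.

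Three stronger readings are tempting, and the documents do not support them.

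- *The reported improvement will be overstated.* This needs at least one treated subject with no evaluation, and needs such subjects to do worse than those kept. The documents give neither a rate nor reasons for leaving.
- *Early failures disappear from the results.* A subject with one evaluation is kept whatever the compliance, and LOCF carries that value forward. A failure recorded at any evaluation is counted.
- *Unevaluated subjects will be replaced.* The Sample Size row allows that reading, because it counts evaluated subjects, but no replacement rule is stated. That is why both columns are shown above.

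On safety, one could argue that events would be reported for every treated subject in practice, or that recording an event counts as a follow-up evaluation. The synopsis says neither: it defines one set for all data and does not define a follow-up evaluation.

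**Conclusion.** The concern holds as a conditional one. As written, a treated subject with no post-baseline evaluation is outside both primary analyses, and nothing else in the plan brings that subject back. If such subjects had no benefit, each of the first few adds roughly 10 percentage points or more to the overstatement of the mean improvement: 10% to 11% for one, 20% to 25% for two and 30% to 43% for three, the range reflecting whether 10 are evaluated or 10 are treated. It is zero if no such subject occurs or if those excluded would have improved as much as the rest. The safety consequence follows from the scope of the set and needs no assumption about benefit, only that an event occurs in an unevaluated subject. This is a cheap improvement worth making in advance, not a flaw that invalidates the study.

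**What to change.** In Statistical Procedures:

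1. Define the primary efficacy set as every subject in whom study stimulation was started. Where there is no post-baseline VAS, set the change from baseline to zero.
2. Keep the current set as a sensitivity analysis.
3. Analyse AE, SAE and stimulation-induced paresthesia rates in all subjects in whom stimulation was started.
4. Report the numbers started, evaluated and, if any, replaced, with reasons. State in the Sample Size row whether replacement is allowed.

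The cost is about one paragraph of text and one extra analysis, with no new data. If every started subject is evaluated, the two efficacy analyses coincide. Otherwise the reported mean change may be slightly less favourable, and zero change is a conservative value for a subject lost for unrelated reasons; the sensitivity analysis shows how much that matters. Fixing the rule now avoids a choice made after the data are seen that could move the main estimate by about 10% for a single subject.
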